3.3 Efficacy Endpoints and Safety Parameters

All primary and key secondary endpoints are analysed during Period 2, the 4-week double blind period of the study. Other secondary endpoints (for which data are available) are assessed during Period 3 (the randomized withdrawal) and Period 4 (open label active extension).

3.3.1 Primary Efficacy Endpoint

The primary efficacy endpoints are the:

- Body weight (kg): Percent change from baseline (Period 2)
- PWS Hyperphagia Questionnaire: Percent Change from baseline (Period 2)
Overall Score

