3.4. Justification for Study Design changes and Doses after the Interim Analysis

A limited interim analysis of data from this study was completed after ~N=16 PWS patients completed the 4-week double blind period of the study. This analysis, which has not been shared with study participants, study investigators, or Rhythm study personnel involved in the conduct of the study, was primarily designed to assess futility and to allow planning of future studies.

These results do not support futility, but showed promising data for the two primary endpoints (percent weight loss and overall hyperphagia score). As expected, these interim results were not definitive based on the small numbers of patients in each treatment group. However, the limited analyses of the 4-week double blind period (primary efficacy period) and the data from the 2-week, double-blind, randomized withdrawal/crossover period supported that the 0.5 mg daily dose provided minimal efficacy (as expected, as this dose was included to define an ineffective dose). [REDACTED]

Therefore, an additional higher dose of 2.5 mg has been included in this protocol, allowing discontinuation of any additional patients treated at the 0.5 mg daily dose. Doses up to 10 mg have been given in single doses to general obese patients, and the limited toxicity was nausea (and in some cases vomiting (which generally are not symptoms reported in PWS patients, who are very resistant to nausea). Otherwise doses up to 2 mg have been administered for up to 12 weeks in healthy obese volunteers (as outlined in our Investigator Brochure). [REDACTED]

[REDACTED]. Based on the excellent safety profile observed in the first half of the study at doses up to 1.5 mg, the dose for the open label extension phase is being increased to 2.5mg, in order to provide additional experience at that dose in patients with PW.

In addition, unrelated to the interim analysis, Rhythm has been working on a new daily version of the hyperphagia observer-reported-outcomes questionnaire. The FDA guidance on development of these patient- and observer-reported outcomes strongly requests that this data be collected on a daily basis. As a result, Rhythm has worked with a PRO-speciality group to develop a potential [REDACTED] This

amendment will include a very simple questionnaire that has daily look-back period as an exploratory endpoint.

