The Hyperphagia Questionnaire is a 10 item instrument that was specifically designed to measure food-related preoccupations and problems in PWS, as well as the severity of these concerns. Items reflected patient and/or parent reports of hyperphagic symptoms gleaned from ongoing research and clinic programs for persons with PWS and their families. The severity items were based on the definition of symptom-related impairment as operationalized by the American Psychiatric Association⁴⁰. Previous factor analyses identified three robust factors: Hyperphagic Drive (e.g., how persistent in asking for food; how easy to direct away from food); Hyperphagic Behaviors (e.g., how fast or clever in obtaining food, how often steal food), and Hyperphagic Severity (time spent talking about food; extent that food interferes with everyday functioning). Items are rated by care providers on a 5-point scale (1 = not a problem to 5 = a severe and/or frequent problem) and are listed in [Appendix 11.2](#)⁴¹. Raw scores for each factor will be used in data analyses, and the three domains will be summed for an overall summary index of hyperphagia.

Plasma RM-493 and RM-493 antibody concentrations will be summarized, and may be compared to PD endpoints.

Noncompartmental methods will be used to compute PK parameters for RM-493, and will be fully described in a separate PK analysis plan. The parameters computed from the 24-hour profile will include C_{max} , T_{max} , $AUC_{24\text{hour}}$, volume of distribution (Vd), and total clearance (CL);

parameters describing elimination may not be computed due to the limited number of blood samples collected to characterize the elimination profile.

Approved

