4.5 Efficacy Endpoints and Analyses

4.5.1 Primary Efficacy Endpoints

There will be 2 co-primary endpoints analysed.

Percent change from baseline in body weight, and percent change from baseline in the Overall score for the PWS Hyperphagia questionnaire over the 4-week double-blind dosing period (Period 2) will be assessed as co-primary efficacy endpoints.

The **Hyperphagia Questionnaire** is a 10-item instrument designed to measure food-related preoccupations and problems in PWS, as well as the severity of these concerns. Three factors identified from this questionnaire are:

- Hyperphagic Drive (e.g. how persistent in asking for food; how easy to direct away from food; items 1,3,6,9)
- Hyperphagic Behaviors (e.g. how fast or clever in obtaining food; how often steal food; items 2,4,5,8)
- Hyperphagic Severity (time spent talking about food; extent that food interferes with everyday functioning; items 7,10)

Items are rated by care providers on a 5-point scale (1=not a problem to 5=a severe and/or frequent problem). The questionnaire can be found in Appendix 2. Raw scores for each factor will be used in data analyses, and the three domains will be summed for an overall summary index of hyperphagia (maximum overall score of 50). Missing values will not be imputed. If a single item in a factor is missing for a patient, that factor will be missing.

These endpoints will be tabulated by dose group for the FAS and PP populations. There will be no adjustment for multiplicity.

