4.5.2.2 Secondary endpoints

Additional secondary efficacy endpoints will be analysed for the FAS population only. Endpoints include:

- Body weight (kg): Percent Change/Change from baseline (Period 3) (Period 4)
- Body weight (kg): Percent Change/Change from baseline (Period 2/3) for continuous active and Placebo treatments
- PWS Hyperphagia Questionnaire: Percent Change/Change from baseline (Period 3) (Period 4)
- DEXA (body fat): Percent Change/Change from Baseline (Period 4)
- DEXA (body mass): Percent Change/Change from Baseline (Period 4)

The **Body weight (kg) percent change and change from baseline (Period 3) (Period 4)**, will be assessed for Period 3 and for Period 4.

The **Body weight (kg) percent change and change from baseline (Period 2/3)** for continuous active and Placebo treatments only (e.g. 4 treatment groups), will be assessed for Period 2 through Period 3.

[figure not shown]
The **PWS Hyperphagia Questionnaire percent change/change from baseline (Period 3) (Period 4)**, will be assessed for Period 3 and Period 4 with treatment groups corresponding to each period. Summaries will be generated for the Overall score, the 3 PWS domains, and individual questions.

The **DEXA (body fat) percent change/change from baseline (Period 4)**, will be assessed from end of Period 2 (Day 42) to end of Period 4 (Day 70), with treatment groups corresponding to these periods.

The **DEXA (body fat) percent change/change from baseline (Period 4)** will be assessed from end of Period 2 (Day 42) to end of Period 4 (Day 70), with treatment groups corresponding to these periods.

A similar model to that used for the primary endpoint analysis will be used for analysis of all secondary endpoints.

By-patient data listings will be provided.

[figure not shown]
The food related problem questionnaire Percent change/change from baseline (Period 2) (Period 3) (Period 4) will be assessed for each of these time periods between baseline and end of Periods 2, 3, and 4 for the respective treatment groups found in those time periods.

[figure not shown]

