The Food-Related Problems Questionnaire is a tool specifically designed for patients with Prader-Willi Syndrome to rate preoccupation with food, impairment of satiety, difficulty with self-control and other food-related 'challenging' behavior. There are 16 questions on this 7-point Likert scale, with responses from 0 (never) to 6 (always), with a response of 7 (does not apply) included for 6 items on the scale. There are 3 open-ended questions. The maximum possible score is 96 for the total FRPQ, where a higher score indicates a 'worse' condition. See Appendix 3.

[figure not shown]
Along with the total item score, three (3) subscales will be presented for:

[figure not shown]
1. Preoccupation (items 1,5,15)
2. Impairment of satiety (items 8,9,13,14,16)
3. Composite negative behavior (2,4,8; 12,15; 3,7,14)

The individual item score and each subscale will be analyzed by each of the 3 periods, using descriptive statistics for visit and mean changes from baseline for each treatment group. If a single item in a factor is missing for a patient, that factor will be missing.

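### The co-primary hyperphagia endpoint is percent change in a score that runs from 10 to 50, so its size depends on the 1-5 item coding and on baseline; change in points, already planned as key secondary, should take its place.

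*SAP*

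**What the plan says.** SAP 3.3.1 lists "PWS Hyperphagia Questionnaire: Percent Change from baseline (Period 2" for the Overall Score beside percent change in weight. SAP 4.3 states the hyperphagia hypothesis in the same percent form. SAP 4.5.1 confirms as co-primary the "percent change from baseline in the Overall score for the PWS Hyperphagia questionnaire over the 4-week double-blind dosing period (Period 2", and 4.5.1.1 makes percent change the modelled variable, with baseline as a covariate.

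SAP 4.5.1 says that the questionnaire "is a 10-item instrument designed to measure food-related preoccupations and problems in PWS", with items scored "1=not a problem to 5=a severe and/or frequent problem". It gives 50 as the highest Overall Score and does not mention the lowest.

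Change in points for the Overall Score is a key secondary endpoint in Period 2 (SAP 3.3.2.1 and 4.5.2.1). Those sections ask for both percent change and change for the three domains and for single questions. SAP 4.5.2.2 extends both forms, down to single questions, to Periods 3 and 4.

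For the Food-Related Problems Questionnaire, SAP 4.5.2.2 says "The food related problem questionnaire Percent change/change from baseline (Period 2) (Period 3) (Period 4) will be assessed". Its items are scored "with responses from 0 (never) to 6 (always".

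The protocol does not state how hyperphagia change is to be expressed. Section 2.2 attaches percentages to weight and DEXA only. Section 3.4 names "the two primary endpoints (percent weight loss and overall hyperphagia score", and section 8.5 says "Raw scores for each factor will be used in data analyses, and the three domains will be summed for an overall summary index of hyperphagia".

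**The concern.** Percent change is natural for weight, where zero means none. On the Overall Score the absence of any problem is coded 10, so dividing by baseline mixes the amount of hyperphagia with a constant set by the coding. Coding the same answers 0 to 4 would change every patient's percentage, and by a different factor for each patient.

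Two consequences follow. The reported percent reduction cannot be read as the share of hyperphagia removed. And for the same improvement in points, patients with low baselines count for more. Protocol 4.2 and 4.3 set no minimum hyperphagia score at entry, so low baselines are possible. SAP 1 says that the study is meant to settle questions about tools and endpoints and to inform Phase 3. An effect size tied to item coding and baseline mix carries over poorly to that purpose.

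**Working it through.** **The plan's own figure.** The only power statement (SAP 4.1, Protocol 8.1) concerns weight in kg. With SDs 1.1 and 2.3 and 12 per arm, SE = √(1.1²/12 + 2.3²/12) = 0.736 on 15.8 Satterthwaite df. A one-sided 0.05 unequal-variance t-test gives 94.5% power at 2.5 kg (stated 94%), 83.0% at 2 kg (stated 83%) and a smallest significant difference of 1.29 kg (stated 1.3). These figures reproduce, but they do not cover hyperphagia.

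**Range of the score.** Ten items scored 1 to 5 (SAP 4.5.1) give 10 × 1 = 10 to 10 × 5 = 50.

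**Dependence on baseline and coding.** For baseline b, a 5-point fall is -500/b percent as coded. With the same answers coded 0 to 4 it is -500/(b - 10) percent. The ratio of the two is b/(b - 10). Complete resolution as coded is -100(b - 10)/b percent.

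| Baseline b | 5-point fall, coded 1-5 | Same answers, coded 0-4 | Ratio | Complete resolution, coded 1-5 |
|---|---|---|---|---|
| 15 | -33.3% | -100% | 3.0 | -33.3% |
| 20 | -25.0% | -50.0% | 2.0 | -50.0% |
| 30 | -16.7% | -25.0% | 1.5 | -66.7% |
| 40 | -12.5% | -16.7% | 1.33 | -75.0% |

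From 45, complete resolution is 35/45 = -78%. In points, the 5-point fall is -5 in every row under either coding.

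**The coding can change an ordering.** A fall from 20 to 17 is -15.0% and one from 40 to 33 is -17.5% as coded. Coded 0 to 4 they are -30.0% and -23.3%, so the order reverses. The same happens to group means:

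- Arm A (20 to 17, 40 to 30): mean -20.0% as coded, -31.7% coded 0-4, -6.5 points.
- Arm B (20 to 15, 40 to 34): mean -20.0% as coded, -35.0% coded 0-4, -5.5 points.

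The arms tie as coded, B is ahead under 0-4 coding, and A is ahead in points.

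**The baseline covariate does not remove this.** If treatment lowers every score by δ points, the percent effect is 100δ/b. It is 40/15 = 2.67 times as large at 15 as at 40. That is a treatment-by-baseline interaction, and the model in SAP 4.5.1.1 has only a main effect for baseline. The optional split at the median hyperphagia score (SAP 4.6) would then show a subgroup difference in percent where none exists in points.

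**Single items.** A move from 1 to 2 is +100%, from 2 to 1 is -50%, and from 5 to 4 is -20%, although each is one step.

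**Power, under assumed inputs.** Three sets of simulations compared points with percent change as coded, one-sided at 0.05:

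- Baseline-adjusted analysis (baseline mean 25, SD 8; change SD 5; effect 5 points): 0.71 against 0.68 with 12 v 12, and 0.63 against 0.61 with 12 v 8.
- Unadjusted comparison, 12 per arm, SD 5, effect 4 points, baselines uniform on 20-40: 60% against 59%.
- The same with baselines uniform on 12-45: 58% against 55%.

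**The case against.** The strongest reply is that little hangs on the label. Change in points is already planned for the Overall Score in both the FAS and the PP set, by similar methods. There is no multiplicity adjustment (SAP 4.2.4), so swapping primary and key secondary moves no alpha, and both results would be reported anyway. Nothing shows that near-floor patients were enrolled. Changing a primary endpoint after an interim look also invites the question whether the data drove it. All of this stands. It limits the size of the point and means the reason must be documented, but it does not make the percent figure independent of the coding.

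Four stronger readings are not supported:

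- A reader might infer that the co-primary endpoint can be undefined. It cannot: the Overall Score is never below 10 and no item is below 1.
- A reader might infer that percent change contradicts the protocol, because of "Raw scores for each factor will be used in data analyses, and the three domains will be summed for an overall summary index of hyperphagia". SAP 4.5.1 makes the same statement in the section that sets percent change as co-primary. It describes how factors are scored and summed, not how change is expressed.
- A reader might infer division by zero throughout the Food-Related Problems Questionnaire. SAP 4.5.2.2 describes its item and subscale analysis as descriptive, with mean changes, so the percent instruction rests on one sentence about the questionnaire as a whole. Its total is 0 only if no applicable item scores above never.
- A reader might infer a material loss of power. The simulations show very little.

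**Conclusion.** The point holds as one of interpretation and of weighting by baseline. The same 5-point improvement counts 2.67 times as much at a baseline of 15 as at 40, and complete resolution is anything from -33% at 15 to -78% at 45. These figures follow from the scale alone.

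How far the trial's result would be affected depends on the spread of baseline scores, which the documents do not give. The power difference of about 1 to 3 percentage points rests wholly on assumed baselines, SDs and effects. It is not a reason in itself to change the endpoint.

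Neither document justifies percent change on this scale, and a measure free of the coding is already planned. The change is worth making.

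**What to change.** - In SAP 3.3.1, 4.3 and 4.5.1 (with 4.5.1.1), make change from baseline in Overall Score, in points, the co-primary hyperphagia endpoint, with the same model and baseline covariate.
- In SAP 3.3.2.1 and 4.5.2.1, list percent change of the Overall Score as secondary, so that both are reported.
- In SAP 3.3.2.1, 4.5.2.1 and 4.5.2.2, delete percent change for individual Hyperphagia items.
- In SAP 4.5.2.2, specify change in points for the Food-Related Problems Questionnaire. This agrees with the mean changes already described there for items and subscales.
- Keep percent change for weight.
- Record the reason as scale-based and fix the change before final unblinding. Protocol 3.4 reports that the interim analysis covered this endpoint.

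The cost is SAP wording and a dated rationale, with the interim hyperphagia result set beside the points analysis. The replacement analysis is already planned, so no data collection or sample size changes.

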3.3.2 Secondary Efficacy Endpoints

[figure not shown]
3.3.2.1 Key secondary efficacy endpoint:

- Body weight (kg): Change from baseline (Period 2)
- PWS Hyperphagia Questionnaire: Percent Change/Change from baseline (Period 2)
 - Overall Score (Change from Baseline only – Period 2)
 - 3 domains
 - Hyperphagic Drive
 - Hyperphagic Behaviors
 - Hyperphagic Severity
 - Individual Questions
- DEXA (body fat): Percent Change/Change from Baseline (Period 2)
- DEXA (body mass): Percent Change/Change from Baseline (Period 2)

3.3.2.2 Additional Secondary endpoints are:

- Body weight (kg): Percent Change/Change from baseline (Period 3) (Period 4)

- Body weight (kg): Percent Change/Change from baseline (Period 2/3) for continuous active and continuous placebo treatments
- PWS Hyperphagia Questionnaire: Percent Change/Change from baseline (Period 3) (Period 4)
- DEXA (body fat): Percent Change/Change from Baseline (Period 4)
- DEXA (body mass): Percent Change/Change from Baseline (Period 4)

3.3.4 Safety Endpoints

Safety and tolerability of RM-493 will be assessed throughout the study.

Safety and tolerability endpoints include:

- AE review
- Injection Site Evaluation
- Clinical laboratory safety tests (subset) including:
 - Hematology: Hemoglobin, Hematocrit, WBC, Platelets
 - Chemistry: Bun, Creatinine, Potassium, ALT, AST, Total Bilirubin, Alkaline phosphatase, GGT, CPK, Glucose
- Vital signs

- ECG evaluations
- Physical examination, Comprehensive Skin Examination, and Height
- Concomitant medication

3.3.5 Pharmacokinetic Endpoints

Blood samples for measurement of plasma RM-493 will be collected from all patients on Day 1 pre-dose and within 5 minutes before study drug is administered on Day 42. Additionally, in a subset of patients participating in the optional PK substudy, (any day from Day 63 through Day 69), PK samples may be collected pre-dose and at selected time points for up to 24 hours post-dose. Samples will be assayed for RM-493 levels. PK analysis will be included in a separate PK analysis plan.

3.4 Analysis Populations

The following patient populations will be evaluated and used for presentation and analysis of the data.

Safety Set (SAF): All subjects who were randomized and received at least 1 dose of study medication and have at least one post-dose safety assessment (within Period 2) will comprise the SAF. Subjects will be classified into groups based on actual treatment received. The SAF will be used for all safety analyses.

Intent to Treat (ITT): All randomized subjects. If there is a greater than 15% difference from the FAS, efficacy tables for the ITT population will also be generated.

Full Analysis Set (FAS): All randomized subjects who have received at least 1 dose of randomized study medication with a baseline and at least 1 post-baseline efficacy observation within Period 2 will comprise the FAS. Subjects will be classified based on randomized treatment group, regardless of the actual treatment taken. The FAS will be used for analyses of all efficacy endpoints.

Per Protocol Set (PP): A subset of the FAS who completed the 4-week double blind treatment period (Period 2) with no major protocol violations. The list of deviations that will exclude data from the PP population will be finalized by the Sponsor and **documented prior to any unblinding of data** for analysis.

Major protocol violations may include, among others:

1. Violation of key inclusion/exclusion criteria, as reviewed by study clinician.
2. Violation of legal documents including, but may not be limited to informed consent and patient privacy.
3. Subjects who received the wrong treatment or incorrect dose.
4. Non-compliance on study withdrawal criteria:

- a. Non-adherence to study drug regimen (must be at least 67% compliant with study medication) or protocol requirements.
- b. Non-compliance with instructions or failure to return for follow-up.

Subjects will be classified based on randomized treatment group, regardless of the actual treatment taken.

The FAS Population is the primary population for the analysis of efficacy parameters. The PP subset is also used for the primary and key secondary endpoint analyses. The SAF is the primary population for the analysis of safety endpoints.

4 STATISTICAL METHODS

This SAP may not describe all analyses that will be performed for this study. Additional analyses may be requested by the Sponsor and performed to supplement the results outlined in this SAP. All post-hoc analyses that have not been identified in this plan but are included in the clinical study report (CSR) will be clearly identified in the text of the CSR.

4.1 Sample Size Justification

Prior data from the 4 week Phase 1b treatment arms of Study RM493-002 (MAD study) yielded the following summary statistics for mean change from baseline after 4 weeks:

Pooled SD for Placebo:	SD=1.1, N=12
Pooled SD for RM493:	SD=2.3, N=18

Assuming SD=1.1 for placebo and SD=2.3 for RM-493, if the true mean difference in 1-month weight loss between treatments is 2.5 kg in this study (N=12 placebo and N=12 RM493), there would be 94% power to yield a statistically significant (alpha=0.05, 1-sided) difference between treatments (83% power if true difference is 2 kg). The minimum observed difference in mean weight loss after 4 weeks of treatment, between RM493 and placebo that would be statistically significant is 1.3 kg.

4.2 General Considerations

Data will be described and analyzed using the Statistical Analysis System (SAS), version 9.2 or higher on a Windows platform (SAS Institute Inc., Cary, NC). Adverse events and medical history will be coded using MedDRA Version 18.1. Prior and concomitant medications will be coded to provide Anatomical Therapeutic Chemical (ATC) levels 2 (therapeutic main groups) and 4 (chemical subgroups) using the December 2014 version of the World Health Organization (WHO) Drug Dictionary.

Individual patient data will be presented in by-patient data listings. Descriptive statistics (number of patients [n], mean, standard deviation [SD], median, minimum [Min] and maximum [Max]) will be presented for continuous data. For categorical data, the frequency and percentage of patients in each category will be presented; percentages will be based on the number of patients with non-missing observations.

Unscheduled visits will not be used, unless they meet the criteria for a baseline observation (e.g. last observation prior to initial double-blind drug administration).

A by-patient listing will be provided which includes all derived efficacy data for which the derivation is not otherwise provided. The data as collected will be provided in the relevant by-patient listing of the raw data.

Unless specified otherwise, by-patient listings will be provided for all data as contained in the raw database.

Reporting of treatment groups in summary tables will be performed with placebo groups (high and low dose groups) combined. The primary focus for the treatment group analysis will be on Period 2 (the 4-week double blind period). Additional analyses will focus on specific intervals (Period 3; effect of randomized change in treatment from active to placebo, and placebo to active); Period 4 (the open label, 1.5 mg dose 2-week active extension), and Period 1 (the double-blind, placebo controlled run-in period).

The final study analysis will include summaries from pooled data using identical active doses (e.g., 0.5 mg, 1.5 mg, 2.5 mg) across the whole study, including data from before and after any interim analysis. As mentioned above, all placebo data will be pooled as well.

Supplemental exploratory analyses will be done for Period 1 (run-in) data to help in understanding of the variability of PWS subjects in a clinical trial; this data will complement the placebo data obtained later in the trial.

Lastly, if the data support that all active groups show similar efficacy, a pooled “active” vs placebo exploratory analysis will also be conducted.

The design of this study raises additional questions on data analysis, as patients may have alternating period of active and placebo treatment after beginning double-blind treatment in Period 2. Data may be summarized by periods and treatment sequences (e.g., within the “withdrawal” phase of Period 3 and/or the open label active extension of Period 4), by focus on patients who remain on the same treatment vs. those whose treatment changes (e.g., to evaluate the difference in hyperphagia in those who remain on an active dose in both Period 2 and 3, vs those that receive active in Period 2 but are withdrawn to placebo in Period 3). It is anticipated that some of these exploratory analyses will be informed by the interim analysis.

